9.3.2 Exclusion Criteria

Subjects who meet any of the following criteria will be excluded from this study:

1. Subjects who have had or are planning to have the following invasive procedures:
 - Major surgical procedure, laparoscopic procedure, open biopsy or significant traumatic injury within 28 days prior to enrollment.
 - Central line placement or subcutaneous port placement is not considered major surgery. External central lines must be placed at least 3 days prior to enrollment and subcutaneous ports must be placed at least 7 days prior to enrollment.
 - Fine needle aspirate within 7 days prior to enrollment.
 - Surgical or other wounds must be adequately healed prior to enrollment.

NOTE: For purposes of this study, bone marrow aspirate and biopsy are not considered surgical procedures and therefore are permitted within 14 days prior to start of protocol therapy.

2. Subjects who have non-healing wound, unhealed or incompletely healed fracture, or a compound (open) bone fracture at the time of enrollment
3. Subjects having an active infection requiring systemic therapy
4. Subjects with a known history of active hepatitis B (defined as hepatitis B surface antigen reactive or hepatitis B virus-DNA detected) or known active hepatitis C virus (HCV, defined as HCV-RNA detected). Note: No testing for hepatitis B and hepatitis C is required unless mandated by the local health authority.
5. Known to be human immunodeficiency virus (HIV) positive. Note: HIV testing is required at screening only when mandated by the local health authority
6. Clinical evidence of nephrotic syndrome prior to enrollment
7. Gastrointestinal bleeding or active hemoptysis (bright red blood of at least half teaspoon) within 21 days prior to enrollment
8. Thrombotic/ thromboembolic event requiring systemic anticoagulation within 90 days prior to enrollment
9. Evidence of new intracranial hemorrhage of more than punctate size on MRI assessment obtained within 28 days prior to study enrollment for subjects with high-grade glioma
10. Diagnosis of lymphoma
11. Radiographic evidence of major blood vessel invasion/infiltration.

12. Evidence of untreated CNS metastases (exception: subjects with primary CNS tumors and leptomeningeal disease).
13. Subjects who are currently receiving enzyme-inducing anticonvulsants
14. Subjects chronically receiving strong cytochrome P450 3A4 (CYP3A4)/ P-glycoprotein (P-gp) inhibitors or inducers within 7 days prior to study enrollment (See [Appendix 15](#) for a list of strong inhibitors and inducers).
15. Females who are breastfeeding or pregnant at Screening or Baseline (as documented by a positive β -hCG [or hCG] test with a minimum sensitivity of 25 IU/L or equivalent units of β -hCG [or hCG]). A separate baseline assessment is required if a negative screening pregnancy test was obtained more than 72 hours before the first dose of study drug.
16. Females of childbearing potential* who:
 - do not agree to use a highly effective method of contraception for the entire study period and for 8 weeks after study drug discontinuation, ie,:
 - total abstinence (if it is their preferred and usual lifestyle)
 - an intrauterine device (IUD) or hormone releasing system (IUS)
 - a contraceptive implant
 - an oral contraceptive** (with additional barrier method)

OR

- do not have a vasectomized partner with confirmed azoospermia.

For sites outside of the EU, it is permissible that if a highly effective method of contraception is not appropriate or acceptable to the subject, then the subject must agree to use a medically acceptable method of contraception, ie, double barrier methods of contraception such as condom plus diaphragm or cervical/vault cap with spermicide.

NOTES:

*All females will be considered to be of childbearing potential unless they are postmenopausal (amenorrheic for at least 12 consecutive months, in the appropriate age group, and without other known or suspected cause) or have been sterilized surgically (ie, bilateral tubal ligation, total hysterectomy, or bilateral oophorectomy, all with surgery at least 1 month before dosing), or are pre-menarcheal (Tanner Stage 1-3).

Must be on a stable dose of the **same oral hormonal contraceptive product for at least 4 weeks before dosing with study drug, for the duration of the study, and for at least 8 weeks after study drug discontinuation.

17. Males who have not had a successful vasectomy (confirmed azoospermia) or if they and their female partners do not meet the criteria above (ie, not of childbearing potential or practicing highly effective contraception throughout the study period and for 7 days after lenvatinib discontinuation or 4 weeks after discontinuation of everolimus). No sperm donation is allowed during the study period and for 7 days after lenvatinib discontinuation or 4 weeks after discontinuation of everolimus.

9.3.3 Removal of Subjects From Therapy or Assessment

The investigator may discontinue treating a subject with study treatment or withdraw the subject from the study at any time for safety or administrative reasons. The subject may decide to discontinue study treatment or withdraw from the study at any time for any reason.

The reason for discontinuation will be documented. If a subject discontinues study treatment, the subject will enter the Follow-Up Period and complete survival follow-up unless the subject withdraws consent. The investigator should confirm whether a subject will withdraw from study treatment but agree to continue protocol-specified, off-treatment study visits, procedures, and survival follow-up, or whether the subject will withdraw consent. If a subject withdraws consent, the date will be documented in the source documents. The Subject Disposition CRF will be completed indicating the primary reason for discontinuation and all other reason(s) contributing to the subject's discontinuation from treatment. In addition, the date of last dose of study drug(s) will be recorded on the Study Medication CRF.

9.4 Treatment

9.4.1 Treatment Administered

Lenvatinib will be provided as hard capsules containing 1 mg, 4 mg, or 10 mg lenvatinib. An extemporaneous suspension of lenvatinib capsules should be used for children unable to swallow capsules ([Appendix 12](#)).

Everolimus will be provided as 2 mg, 3 mg, and 5 mg dispersible tablet formulations (everolimus tablets for oral suspension).

Lenvatinib and everolimus will be administered orally on a once daily schedule in continuous 28-day cycles. The sequence of administration is not important. Dosing nomograms based on BSA and dose level will be used to prescribe lenvatinib and everolimus for subjects to minimize inter-subject dosing variability. The maximum daily dose of lenvatinib administered during the study should not exceed 18 mg in Dose Levels -1, and 1, and 24 mg in Dose Levels 2 and 3. The maximum daily dose of everolimus should not exceed 5 mg in Dose Levels -1, 1, and 2, and 7 mg in Dose Level 3. Intra-subject titration of everolimus will not be allowed on this study. Intra-subject dose escalation of both lenvatinib and everolimus will not be allowed.

Subjects benefiting from study treatment in the opinion of the investigator will continue treatment until disease progression, development of unacceptable toxicity, withdrawal of consent or are withdrawn from the study for any reason, or termination of the study by the sponsor.

9.4.1.1 Study Treatment Dose Reduction and Interruption Instructions

Dose reduction and interruptions for subjects who experience lenvatinib-everolimus combination therapy-related toxicity will be managed as described in [Table 5](#). Investigators will decide the probability of the event being related to protocol therapy as to whether dose modification of drug therapy is required.

Doses in the Dose Adjustment column are based on a presumed starting dose of 11 mg/m² lenvatinib and 3 mg/m² everolimus. Dose reductions will occur in succession based on the previous dose level. Each dose level reduction due to toxicity at a given BSA is

approximately 25% reduction from the previous dose. Once the study drug dose has been reduced, it may not be increased at a later date, unless the dose was mistakenly decreased; in this situation, the sponsor's approval is required to increase the dose.

Asymptomatic laboratory abnormalities, including Grade ≥ 3 abnormalities (eg, elevations of amylase and lipase) that are not considered clinically relevant by the investigator, should be managed per institutional guidelines; continuation of treatment should be discussed with the sponsor.

Table 5 Dose Modification Guidelines for Lenvatinib-Everolimus Combination Treatment-Related Toxicity

Treatment-Related Toxicity ^{a,b}	Management	Dose Adjustment
Grade 1 or Tolerable Grade 2		
	Continue treatment	No change
Intolerable Grade 2^{c, d, e} or Grade 3^f		
First occurrence	Interrupt lenvatinib and everolimus until resolved to Grade 0-1 or tolerable Grade 2	Reduce lenvatinib dose to 8 mg/m ² (or approximately 25% reduction of the starting dose) orally once a day (one-level reduction) and resume everolimus at the same dose as prior to dose interruption
Second occurrence (same toxicity or new toxicity)	Interrupt lenvatinib and everolimus until resolved to Grade 0-1 or tolerable Grade 2	Reduce lenvatinib dose to 6 mg/m ² (or approximately 25% reduction from the previous dose level) once a day (one-level reduction). Dose reduction of everolimus to 3 mg/m ² every other day may be considered for Grade 3 toxicity ^e
Third occurrence (same toxicity or new toxicity)	Interrupt lenvatinib and everolimus until resolved to Grade 0-1 or tolerable Grade 2	Reduce lenvatinib dose to 4.5 mg/m ² (or approximately 25% reduction from the previous dose level) orally once a day (1-level reduction). Dose reduction of everolimus for Grade 3 toxicity: i) if 3 mg/m ² daily everolimus at event onset, reduce to 3 mg/m ² every other day or

		ii) if 3 mg/m ² every other day everolimus at event onset, discontinue
Fourth occurrence (same toxicity or new toxicity)	Interrupt lenvatinib and everolimus	Discuss with sponsor
Grade 4^g: Discontinue Study Treatment		

Note: For grading see Common Terminology Criteria for Adverse Events (CTCAE) v4.03. Collect all CTC grades of adverse events, decreasing and increasing grade.
 
a: An interruption of study treatment for more than 28 days will require sponsor’s approval before treatment can be resumed.
 
b: Initiate optimal medical management for nausea, vomiting, hypothyroidism and/or diarrhea prior to any study treatment interruption or dose reduction.
 
c: Applicable only to Grade 2 toxicities judged by the subject and/or physician to be intolerable.
 
d: Obese subjects with weight loss do not need to return to the baseline weight or 10% of baseline weight (ie, Grade 1 weight loss). These subjects will restart the study drug(s) at a lower dose once their weight remains stable for at least 1 week and they reached the normal body mass index (BMI; if the weight loss occurred but it is still above normal BMI, they can restart the study treatment at a lower dose once the weight has been stable for at least 1 week). Normal BMI should be used as the new baseline for further dose reductions. See BMI charts for boys (Appendix 9) and girls (Appendix 10).
 
e: For Grade 2 toxicity, resume everolimus at the same dose as prior to dose interruption. For Grade 3 toxicity, investigator will decide the probability of the event being related to one or both drugs as to whether dose modification of one or both drugs is required.
 
f: For asymptomatic laboratory abnormalities, such as Grade ≥3 elevations of amylase and lipase that are not considered clinically relevant by the investigator, continuation of treatment should be discussed with the sponsor.
 
g: Excluding laboratory abnormalities judged to be non-life-threatening, in which case manage as Grade 3.
		

9.4.1.2 Blood Pressure

For children, BP varies by the sex and age of the child and it is closely related to height and weight. BP will be assessed in terms of percentile for sex, age and height/length. Guidelines to sex, age, and height-specific percentiles of BP are provided in [Appendix 7](#) and [Appendix 8](#). BP that is consistently above the 95th percentile [for subjects age 18-21 years BP ≥140/90 mmHg] for age and height/length requires further evaluation. A referral to a cardiologist is recommended for subjects who develop hypertension during the study. Ideally, cardiovascular assessments and the management of hypertension should be supervised by a cardiologist. Exercise, excitement, coughing, crying and struggling may raise the systolic pressure of children as much as 40 to 50 mmHg greater than their usual level. Variability in BP in children of approximately the same age and body build should be expected and serial measurements should always be obtained when evaluating a subject with hypertension. **BP values for management of hypertension for subjects 18 to 21 years of age are included in parenthesis.**

9.4.1.3 Management of Hypertension

Hypertension is a recognized side-effect of treatment with drugs inhibiting VEGF signaling. Investigators should therefore ensure that subjects enrolled to receive treatment with lenvatinib have BP <95th percentile [BP ≤150/90 mmHg] for sex, age, and height/length at the time of study entry and, if known to be hypertensive, have been on a stable dose of antihypertensive therapy for at least 1 week before Cycle 1 Day 1. Early detection and

effective management of hypertension are important to minimize the need for dose interruptions and reductions. Antihypertensive agents should be started as soon as elevated BP (systolic BP \geq 95th percentile [BP \geq 140 mmHg] or diastolic BP \geq 95th percentile [BP \geq 90 mmHg]) is confirmed on 2 assessments obtained 1 hour apart. One BP assessment is defined as the mean value of 3 measurements obtained at least 5 minutes apart. The choice of antihypertensive treatment should be individualized to the subject's clinical circumstances and follow standard medical practice. For previously normotensive subjects, monotherapy with one of the classes of antihypertensives should be started when systolic BP \geq 95th percentile [BP \geq 140 mmHg] or diastolic BP \geq 95th percentile [BP \geq 90 mmHg] is first observed on 2 assessments obtained 1 hour apart. For those subjects already on antihypertensive medication, the dose of the current agent may be increased, if appropriate, or 1 or more agents of a different class of antihypertensive should be added. For subjects with hypertension and proteinuria, treatment with an angiotensin-converting enzyme (ACE) inhibitor or angiotensin-II receptor antagonist is preferred.

Study treatment should be withheld in any instances where a subject is at imminent risk to develop a hypertensive crisis or has significant risk factors for severe complications of uncontrolled hypertension (eg, BP \geq 99th percentile [BP \geq 160/100 mmHg], significant risk factors for cardiac disease, intracerebral hemorrhage, or other significant comorbidities). Once the subject has been on the same antihypertensive medications for at least 48 hours and the BP is controlled, study treatment should be resumed as described below.

During the Treatment Period, subjects with systolic BP \geq 99th percentile [BP \geq 160 mmHg] or diastolic BP \geq 99th percentile [BP \geq 100 mmHg] must have their BP monitored every 2 weeks (on Day 15 or more frequently as clinically indicated) until systolic BP has been $<$ 95th percentile [\leq 150 mmHg] and diastolic BP has been $<$ 95th percentile [\leq 95 mmHg] for 3 consecutive months. If a new event of systolic BP \geq 99th percentile [BP \geq 160 mmHg] or diastolic BP \geq 99th percentile [BP \geq 100 mmHg] occurs, the subject must resume the Day 15 evaluation until systolic BP has been $<$ 95th percentile [\leq 150 mmHg] and diastolic BP has been $<$ 95th percentile [\leq 95 mmHg] for 3 consecutive months.

The following guidelines should be followed for the management of systolic BP \geq 99th percentile [BP \geq 160 mmHg] or diastolic BP \geq 99th percentile [BP \geq 100 mmHg] confirmed on repeat measurements after an hour:

- Continue study treatment and institute antihypertensive therapy for subjects not already receiving antihypertensive medication.
- For those subjects already on antihypertensive medication, the dose of the current agent may be increased, if appropriate, or 1 or more agents of a different class of antihypertensive should be added.
- If systolic BP \geq 99th percentile (BP \geq 160 mmHg) or diastolic BP \geq 99th percentile (BP \geq 100 mmHg) persists despite maximal antihypertensive therapy, then study treatment administration should be interrupted and restarted at a lower dose once daily (one dose level reduction as specified in [Table 5](#)) only when systolic BP $<$ 95th percentile (BP \leq 150 mmHg) and diastolic BP $<$ 95th percentile (BP \leq 95 mmHg).

≤95 mmHg) and the subject has been on a stable dose of antihypertensive medication for at least 48 hours.

- If systolic BP ≥99th percentile (BP ≥160 mmHg) or diastolic BP ≥99th percentile (BP ≥100 mmHg) recurs despite optimal management of hypertension with antihypertensive medications (either by dose increase or the addition of a different class of antihypertensive), then study treatment administration should be interrupted and restarted at a lower dose once daily (one dose level reduction as specified in the [Table 5](#)) only when systolic BP <95th percentile (BP ≤150 mmHg) and diastolic BP <95th percentile ([BP ≤95 mmHg] and the subject has been on a stable dose of antihypertensive medication for at least 48 hours.
- If systolic BP ≥99th percentile ([BP ≥160 mmHg) or diastolic BP ≥99th percentile ([BP ≥100 mmHg] recurs despite optimal management of hypertension with antihypertensive medications (either by dose increase or the addition of a different class of antihypertensive), then study treatment administration should be interrupted and a restart of treatment should be discussed with the sponsor.

The following guidelines should be followed for the management of Grade 4 hypertension (life-threatening consequences):

- Institute appropriate medical management
- Discontinue study treatment

[Figure 2](#) shows the procedures associated with the management of hypertension.

[figure not shown]

Figure 2 Management of Hypertension

BP = blood pressure, HTN = hypertension, Tx = treatment.

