- Any Grade 3 or greater non-hematological toxicity attributable to the investigational drug with the specific **exclusion** of:
 - Grade 3 nausea and vomiting <3 days duration
 - Grade 3 diarrhea <3 days duration
 - Grade 3 weight loss
 - Grade 3 liver enzyme elevation, including ALT/aspartate aminotransferase (AST)/ gamma glutamyl transferase (GGT)/ bilirubin/alkaline phosphatase that returns to Grade ≤ 1 or baseline within 7 days
 - Grade 3 asymptomatic elevation in amylase or lipase that returns to Grade ≤ 1 or baseline within 7 days
 - Grade 3 elevation in triglycerides that returns to Grade ≤ 1 or baseline within 7 days
 - Grade 3 or 4 fever <5 days duration
 - Grade 3 infection <5 days duration
 - Grade 3 hypophosphatemia, hypokalemia, hypocalcemia or hypomagnesemia responsive to oral supplementation
 - Grade 3 proteinuria (UPC) ratio >1.9 unless confirmed with a second measurement within 72 hours
 - Grade 3 headache <3 days duration responsive to optimal management.

- Any Grade 2 non-hematological toxicity that persists for ≥ 7 days and is considered sufficiently medically significant or sufficiently intolerable by subjects despite optimal supportive care that it requires treatment interruption.
- Any dose interruption or reduction due to toxicity which results in administration of less than 75% of the planned dosage of lenvatinib and/or everolimus.
- Note: Allergic reactions that necessitate discontinuation of study drug will not be considered a DLT.
- **Dose-limiting hypertension:**
 - Any Grade 4 hypertension

Confirmed systolic or diastolic BP more than 25 mmHg above 95th percentile for sex, age, height/length, or an elevated diastolic BP (ie, >95th percentile for age) not controlled by a single antihypertensive medication within 14 days of use. An antihypertensive tablet or capsule that contains up to 2 antihypertensive ingredient medications will be considered a single antihypertensive medication.

B. Hematological DLT:

- In subjects evaluable for hematological toxicity, DLT is defined as:
 - Grade 4 thrombocytopenia (platelet count $< 25,000/\text{mm}^3$) or Grade 4 neutropenia, not due to malignant infiltration.
- Any \geq Grade 2 arterial thromboembolic events (including cerebrovascular ischemia, peripheral or visceral arterial ischemia).
- Note: Grade 3 or 4 febrile neutropenia will not be considered a DLT.

All DLTs must be reported to the sponsor within 24 hours of their occurrence.

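### Protocol 9.4.1.3 names blood pressure at or above the 99th percentile as a reason to withhold study treatment, yet tells sites to continue it at that threshold in subjects not on antihypertensives, and the text sets no precedence

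*Protocol*

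**What the plan says.** Protocol 9.4.1.3 contains two sets of instructions that meet at one threshold.

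- **Withhold.** "Study treatment should be withheld in any instances where a subject is at imminent risk to develop a hypertensive crisis", or where the subject "has significant risk factors for severe complications of uncontrolled hypertension". The examples in brackets open with BP at or above the 99th percentile and run on, after the adult value, as "160/100 mmHg], significant risk factors for cardiac disease, intracerebral hemorrhage, or other significant comorbidities". Treatment resumes "Once the subject has been on the same antihypertensive medications for at least 48 hours and the BP is controlled".
- **Continue.** A list of guidelines follows for systolic or diastolic BP at or above the 99th percentile, confirmed on repeat measurement after an hour. Its first item is "Continue study treatment and institute antihypertensive therapy for subjects not already receiving antihypertensive medication". For subjects already on such medication, it provides for raising the dose or adding agents and does not mention stopping study treatment. Interruption comes later: if the BP "persists despite maximal antihypertensive therapy, then study treatment administration should be interrupted and restarted at a lower dose once daily", or if it recurs despite optimal management.

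For ages 18-21 the section gives bracketed adult values beside each percentile. Inclusion criterion 5 limits Phase 1 to subjects under 18, so these brackets concern Phase 2.

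The DLT definition in Protocol 9.1 includes "Any dose interruption or reduction due to toxicity which results in administration of less than 75% of the planned dosage of lenvatinib and/or everolimus". The observation window is Cycle 1, which is 28 days.

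**The concern.** Section 9.4.1.3 itself calls hypertension a recognised effect of drugs that inhibit VEGF signalling, so sites will use these instructions. One paragraph gives a reading at or above the 99th percentile as a ground for withholding. The next set of rules takes a confirmed reading at the same limit and, in subjects not yet on antihypertensives, keeps study treatment going. A site can follow either one and be within the protocol.

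The first thing at stake is that children with the same reading may be handled differently. The second is that the exposure, interruption and dose-modification summaries for a known class toxicity would partly reflect which paragraph a site followed. The third, in Phase 1 only, is a possible effect on DLT classification, because one DLT criterion depends on how much of the planned dose was given.

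**Working it through.** The point rests on text and the plan states no figure to reproduce. I set the instructions side by side and then checked the arithmetic of the DLT route.

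**1. Same threshold, opposite action**

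| | Withhold paragraph | Guideline list |
|---|---|---|
| BP trigger | At or above the 99th percentile (160/100 mmHg) | Confirmed systolic or diastolic at or above the 99th percentile (160 or 100 mmHg) |
| Action on study treatment | Withhold | Continue, if not already on antihypertensives |
| When it changes | Resume after at least 48 hours on the same medication with BP controlled | Interrupt if it persists on maximal therapy or recurs despite optimal management |

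In the withhold paragraph the BP value stands in the list of examples beside cardiac risk, intracerebral hemorrhage and comorbidities. It is not written as a condition to be met in addition to them. Neither part says that it overrides the other.

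**2. Adult equivalents of the 95th percentile in 9.4.1.3 (ages 18-21)**

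| Use | Adult value (mmHg) | Reading of 145/85 |
|---|---|---|
| Study entry | 150/90 or below | Met |
| Start antihypertensives | Systolic 140 or above, or diastolic 90 or above | Met (145 is at least 140) |
| Restart study treatment | Systolic 150 or below and diastolic 95 or below | Met |

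Under the percentile wording, a reading cannot be both below the 95th (restart) and at or above it (start antihypertensives). Under the adult brackets, 145/85 is both.

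**3. Possible DLT effect in Phase 1 Cycle 1**

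Share of planned dose = (28 − days held) / 28, compared with the 75% rule. This assumes the full dose before and after the hold.

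- 2 days held: 26/28 = 92.9%, not a DLT by this route.
- 7 days held: 21/28 = 75.0%, not below 75%, so not a DLT by this route.
- 8 days held: 20/28 = 71.4%, a DLT by this route.

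The documents give no expected length of hold, so 8 days is an assumption. The 48 hours in the text is a minimum and also requires BP to be controlled. A reduced dose after the hold would lower these shares.

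**4. Is there a range where management can decide DLT status?**

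Dose-limiting hypertension in 9.1 needs, among its criteria, a confirmed BP more than 25 mmHg above the 95th percentile. In Appendix 7, a boy aged 10 at the 50th height percentile has a systolic 95th percentile of 119 and a 99th of 127 mmHg. The size criterion is then a reading above 119 + 25 = 144. Systolic readings from 127 to 144 trigger the conflicting instructions without meeting that criterion. In that range, the dose-share route can depend on which instruction was followed. So can the DLT criterion for Grade 2 toxicity that lasts 7 days or more and requires interruption.

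**5. Routes that do not depend on the choice**

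Grade 4 hypertension is a DLT in any case. So is an elevated diastolic BP not controlled by a single medication within 14 days. Hypertension is also absent from the list of exclusions to the general Grade 3 rule. If that rule applies alongside the specific hypertension criteria, Grade 3 events are DLTs under either instruction.

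**The case against.** The best defence is a tiered reading: withholding is for a high-risk subset, continuing is the general rule, and the withhold paragraph links to what follows by referring forward for resumption. That may be what was intended. It does not fit the words, because the 99th-percentile reading is itself one of the examples that place a subject in the subset. Figure 2 is not shown in the copy reviewed and may set the order, but the prose would still need to agree with it.

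The case against a large DLT effect is stronger and largely stands. A reader might infer that the conflict changes DLT counts and hence the MTD, since a level with 1 DLT in 6 would move to 2 in 6. The documents do not support that as a general conclusion:

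- The dose-share route needs a hold of 8 days or more, and nothing in the plan says holds will last that long.
- Continuing treatment does not rule out a DLT, given the other criteria.
- Section 9.1 allows expansion to 12 subjects to be considered when 2 DLTs in 6 are of different classes, subject to conditions.
- DLTs are determined by the investigator and the medical monitor, with the steering committee as needed. That review limits divergence in classification, although it comes after dosing has already differed.

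Nor do the two hypertension DLTs reported in Section 7.3 from the single-agent paediatric study establish a size. One was Grade 4, which leads to discontinuation here, and that study's DLT definition is not given.

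It is also fair that the explicit instruction to continue covers only subjects not already on antihypertensives, and that the three adult values belong to different actions. Different limits for different actions need no defence; labelling all three as the 95th percentile does.

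**Conclusion.** The contradiction is real in the current text: one section, one threshold, and two actions on study treatment for subjects not already on antihypertensives, with no precedence stated in the prose. It deserves correction for patient handling and consistency between sites, whatever its effect on dose finding.

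The inconsistent adult equivalents (150/90, 140/90, 150/95) are a separate and smaller flaw. A reader might link them to the MTD as well, but Phase 1 enrols only subjects under 18.

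The DLT consequence is a conditional possibility confined to Phase 1 Cycle 1. By the dose-share route it requires an assumed hold of at least 8 of 28 days (71.4% against 75%), or less if a reduced dose follows the hold. It also requires an event that no other criterion already makes a DLT. How often that would happen cannot be worked out from the documents. The conclusion on precedence is subject to Figure 2, which could not be checked.

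**What to change.** Reconcile the withhold paragraph and the guideline list in 9.4.1.3 so that one unambiguous instruction applies at or above the 99th percentile. If both are meant to stand, state which takes precedence and for which subjects. Reconcile the adult values given for the 95th percentile, or stop labelling different action limits as the same percentile. Check that Figure 2 agrees with the revised text. Which clinical rule and which limits apply is for the sponsor to decide.

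The cost is protocol clarification wording. It needs no change to the sample size, the endpoints or the DLT definition.
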